2. CHARACTERISTICS OF STUDY POPULATION

2.1 Subject Characteristics

Asthma and its morbidity disproportionately affect minority children of low-income families in inner cities, where asthma severity has increased and poses serious challenges to achieving adequate asthma control.⁵ Disparate burdens of asthma and its adverse outcomes among minority children have been consistently documented in the past 20 years.^{4, 23-25} In 2010, asthma prevalence in black children under 18 years was twice that of white youths; children in families below the poverty threshold as defined by the US Census Bureau were 1.5 times more likely to report current asthma than those in families at or above 200% of the poverty line.² Compared with white youth, black inner-city children are 4 and 3 times more likely to have asthma-related ED visits and hospitalizations respectively.⁴ The three cities where the study will take place, Buffalo, NY; Baltimore MD; Memphis TN demonstrate high rates of pediatric asthma, high health care utilization and high morbidity and mortality rates, thus this study will take place in these cities that are most likely to benefit from a proposed intervention.

a) Number of Subjects:

A total of 378 adolescents (12-17 years) and 42 adolescent peer leaders (16-20 years) will be recruited for this study. The sample size (N=378) is based on the power analysis using a novel method developed by Roy et al.²⁶ for a 3-level hierarchical longitudinal design based on the program "RMASS." This method has the advantage of incorporating three levels from the sites and repeated-measures from each subject with random-effects of the time trends at both the subject- and site-level, which are assumed to be equivalent in terms of sampling proportions, number of groups and differential attrition rates over time. In this proposed study, quality of life, the primary outcome, was used to estimate the sample size. Using data from the previous study,²⁷ the longitudinal trajectories of quality of life and its treatment-by-time interactions based on subject-level randomization were modeled: the estimated treatment*time interaction coefficient was 0.6 units, estimated SDs for error was 15, and the random-slope was 1.76. These estimated values with a Type-I error rate (alpha) of .05 yielded a total sample size of 276 that would detect a

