time trend over eight time points (T1-T8) between groups with a power of .80. This sample size was estimated on the assumption that the analyses use multi-site hierarchical 3-level linear mixed-effects models. In the earlier study, the attrition rate of the inner-city subsample (n=55) was 27% including those who failed to attend the camp program (n=13, 23%) and those lost to follow-up (n=2, 4%). To compensate for a possible attrition rate of 27%, the total sample size was increased to 378 (126 for each site; 63 each of two groups).

b) Gender and Age of Subjects:

Recruitment will not be limited on gender. Based on epidemiological data, we will focus on adolescents from 12-17 years of age for campers and 16-20 years of age for peer leaders.

Participants will be stratified by gender and age (younger 12-14 years, older 15-17 years), which emerged as influential covariates in the PI's earlier study. Within each of four blocks generated by each combination of these two covariates, each subject will be randomly assigned to either group using a computer-generated randomization table. Stratified randomization will ensure a similar number of subjects representing each block in the two treatment groups, balancing the influence of age and gender. Stratified randomization will be done separately for each site, and centrally coordinated and managed. Within the treatment group, participants will be assigned to subgroups based on their age [younger (12-14 years) and older groups (15-17)] to allow the study team to adjust the levels of difficulty/complexity of program content delivered at the camp. In doing so, we will attempt to enhance participants' understanding of the information covered in the program. In the previous study, we found no differences in study outcomes or camp satisfaction between gender-matched groups and co-ed groups, so subgroups will be gender-mixed.

c) Racial and Ethnic Origin:

Enrollment of participants will not be restricted to any racial or ethnic groups. By recruiting participants from three cities with high prevalence and incidence of pediatric asthma, (again based on epidemiological data) we anticipate the sample demographic to have a higher proportion of minority populations representative of the neighborhoods targeted (Buffalo, Baltimore and Memphis.)

d) Vulnerable Subjects:

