4. METHODS AND STUDY PROCEDURES

4.1 Study Procedures and Assessments

Design: This study will use a two-group randomized controlled design implemented in three metropolitan cities: Buffalo, NY, Baltimore, MD, and Memphis, TN. The project coordinator and a research assistant in each city who are not involved in direct patient care of teens with asthma will be responsible for recruitment and consent process taking place in each site. Peer leaders will attend a three-day intense training session that will take place prior to camps, lead small-group instructional activities at a one-day camp (PLASMA group) and follow up their group members bimonthly for 15 months. Camp participants from each site (n=126) will be randomly assigned to the peer-led (PLASMA) group or the adult-led (control) group. Upon enrollment, participants will be stratified by gender and age (younger 12-14 years, older 15-17 years), and randomly assigned to either group within each of four blocks generated by the combination of gender and age strata. Each group will attend a separate day camp where an asthma self-management program will be implemented either by peer leaders (intervention) or healthcare professionals (control). After the camp, the intervention group will receive peer-leader contacts bimonthly for 14 months using phone calls or other communication technologies (e.g., emails, or short-message system (e.g., texting) of teens' choice. Adult instructors (healthcare professionals) will contact the control group bimonthly for 14 months using similar methods, but different contact topics.

Both groups (intervention and control – more details below) will provide data at enrollment (T1), 3 months later (T2), immediately following the camp (T3), and at 3-, 6-, 9-, 12-, and 15-months post-camp (T4-T8).

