10. DATA ANALYSIS AND DATA MONITORING

10.1 Planned Statistical Analysis: Analyses will be performed using SAS, and R⁵⁶ will be used as analysis software to ensure the validity and reproducibility of the results. We will perform descriptive statistics on each outcome measure to look for abnormality and outliers. If a measure is not normally distributed, transformation will be applied. We will identify and investigate outliers for sources of errors, and conduct preliminary analyses on data distribution and bivariate correlations to determine the appropriate statistical model as well as the final interpretation of the results. We will investigate missing data with pattern analysis for data missing completely at random (MCAR), missing at random (MAR) or missing not at random (MNAR), and use statistical methods appropriate for each type such as maximum likelihood and multiple imputation to impute missing values so full analysis can be performed with sensitivity. We will compute Cronbach's alphas for psychometric measures, and assess construct validity using exploratory or confirmatory factor analysis when appropriate. The PLASMA and control groups will be compared on baseline data to determine any systematic differences; if any are found, analyses will include the variables as covariates in the model to adjust for the imbalances.

Aim 1: A multi-site hierarchical three-level linear mixed-effects model,^{26, 56, 57} where level 1 represents repeated measures, level 2 = subject, and level 3 = site, will be used to analyze treatment differences and treatment-by-time interaction described in the following notation by Hedeker and Gibbons.⁵⁷

Aim 2: The mediating effects will be examined mainly using the mediation methods of Baron & Kenny.⁵⁸ When found significant, a multiple mediation analysis⁵⁹ procedure will be used to further determine whether the effect of PLASMA on quality of life is mediated jointly by multiple exploratory outcomes.

Aim 3: Moderating effects will be examined by multiple linear models and generalized linear models described in Berridge and Crouchley⁵⁶ or Chen and Peace⁶⁰ along with the above multi-site hierarchical three-level linear mixed-effects models.

Aim 4: This aim will be tested by applying the multi-site hierarchical two-level linear mixed-effects models described in the analysis for Aim 1, with level 1 representing longitudinal measurements and level 2 sites.

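### Power is claimed for a treatment-by-time trend running from T1 to T8, although the arms cannot diverge until the camp just before T3; at the stated rate, power could be as low as about 58%

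*Combined protocol and SAP*

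**What the plan says.** Section 2.1a takes its inputs from the previous study: "the estimated treatment*time interaction coefficient was 0.6 units, estimated SDs for error was 15, and the random-slope was 1.76". At an alpha of .05 it arrives at 276 evaluable adolescents in total. The target of that calculation is a "time trend over eight time points (T1-T8) between groups with a power of .80". Allowing for 27% attrition, enrolment is set at 378.

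Section 4.1 places the visits at "enrollment (T1), 3 months later (T2), immediately following the camp (T3), and at 3-, 6-, 9-, 12-, and 15-months post-camp (T4-T8". The arms differ in who runs the camp and in the contacts that follow it: "After the camp, the intervention group will receive peer-leader contacts bimonthly for 14 months". Control contacts, from adult instructors, cover the same 14 months.

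Section 10.1 (Aim 1) says that a three-level linear mixed model "will be used to analyze treatment differences and treatment-by-time interaction". The prose of that section gives no time coding relative to the camp.

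**The concern.** A single coefficient applied over T1-T8 describes two arms that separate steadily from enrolment. In this trial nothing differs between the arms until the camp, so their expected scores are equal at T1 and T2 by randomization. The assumed trajectory is one that the design cannot produce.

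Two things are at stake. First, the 80% may belong to a different effect pattern from the one that the trial can show. Secondly, if H1 is tested with one straight-line interaction over T1-T8, the pre-camp visits are fitted as part of the divergence. Its coefficient is then not the post-camp rate of change.

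**Working it through.** **Inputs.** Section 2.1a: coefficient 0.6 (time unit not given), error SD 15, random slope 1.76 (SD or variance not stated outright), alpha .05 (taken as two-sided), N = 276 (138 per arm), power .80. No site-level variance is printed, so it is taken as 0. Section 4.1: camp just before T3. Spacing is 3 months: section 4.4 names a visit 3 months pre-camp, and section 7.2 gives 21 months in all, which is 7 intervals x 3.

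**The plan's own figures.** Attrition agrees: 276/0.73 = 378.08. For a comparison of slopes, N = 4(1.960 + 0.842)² x (slope variance + error variance/Sxx)/0.6², with 4 x 2.8016² = 31.40.

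- Both inputs as SDs, time in months (Sxx = 378): 31.40 x (3.098 + 225/378)/0.36 = about 322. Power at 276 is about 74%.
- Both as SDs, time in visits (Sxx = 42): 31.40 x (3.098 + 225/42)/0.36 = about 738. Power at 276 is about 40%.
- 15 as a variance, 1.76 as an SD, months: 273.6. This is close to 276 but goes against the printed label of 15 as an SD.

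The 80% is therefore not reproduced from the inputs as labelled. The steps below accept it and ask only how it changes with effect shape.

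**Effect shape.** With balanced data and a random intercept and slope, the T1-T8 interaction estimate is the least-squares slope of the between-arm difference on t = 0, …, 7. The ratio to the planned slope is Σ(t − 3.5)y/42. Power is Φ(2.802 x ratio − 1.960). The ratio does not depend on the time unit or on the variances.

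| Between-arm difference at T1-T8, in multiples of 0.6 | Σ(t − 3.5)y | Ratio | Power at 276 |
|---|---|---|---|
| Plan: 0,1,2,3,4,5,6,7 | 42 | 1.000 | 80% |
| Same rate from zero at T3: 0,0,0,1,2,3,4,5 | 32.5 | 0.774 | 58% |
| Same rate from T2: 0,0,1,2,3,4,5,6 | 38.5 | 0.917 | 73% |
| Plan's T8 difference, all as a step at camp: 0,0,7,7,7,7,7,7 | 42 | 1.000 | 80% |
| Plan's T8 difference, linear from T3: 0,0,0,1.4,2.8,4.2,5.6,7 | 45.5 | 1.083 | 86% |

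In the second row the fitted coefficient is 0.774 x 0.6 = 0.46, and power is Φ(2.168 − 1.960) = 0.58. With all 378 followed it is Φ(2.168 x √(378/276) − 1.960) = 0.72.

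**Would recoding time recover the loss?** Take a term coded 0 at T1-T3 and then time since camp, with a matching random slope, N = 276 and both inputs as SDs.

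| True effect | Time unit | Linear T1-T8 term | Time-since-camp term |
|---|---|---|---|
| 0.6 rate from zero at T3 | months | 52% | 70% |
| 0.6 rate from zero at T3 | visits | 26% | 31% |
| Step at camp, 7 intervals' worth | months | 74% | 68% |
| Step at camp, 7 intervals' worth | visits | 40% | 30% |

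This coding helps if the effect builds gradually and hurts if it is immediate.

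**The case against.** The strongest objection concerns the origin of the 0.6. It is an estimated coefficient from an earlier study whose visit times are not given. If that fit already included pre-program visits on a similar schedule, 0.6 is already the averaged linear slope, and applying 0.774 would dilute it twice. The documents do not settle this, and the point stands as a limit on the size of the loss.

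The 58% also requires no difference at T3, yet T3 follows a camp that delivers all three instructional sessions. An early effect raises the figure, as the table shows. This too stands.

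Thirdly, Aim 1 refers to model notation that was not readable in the text available for this review, so post-camp coding in the analysis cannot be excluded. That limits what can be said about the analysis. It does not change the wording of 2.1a, which still describes a trend over T1-T8.

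A reader might go further and infer that the trial's power is 58%, that 276 is wrong, or that the primary test is invalid. The documents support none of these. The 58% rescales an 80% that cannot be verified. The sample-size program may use inputs that are not printed, such as a site-level variance or an attrition pattern. A linear interaction remains a valid test under the null; the 23% attenuation arises only for an effect that starts from zero at T3.

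**Conclusion.** The concern holds in a conditional form. Section 2.1a assumes a between-arm trend over visits at which no effect is possible, and nothing in 2.1a or in the prose of Aim 1 allows for this.

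If the 80% is accepted, visits are 3 months apart, the test is a linear T1-T8 interaction and 0.6 is a post-camp rate, power is about 58% with divergence from T3 and about 73% with divergence from T2. It is about 80% to 86% if the plan's full T8 difference is still reached, although the plan does not state that effect. There is no further loss if 0.6 was already averaged over pre-camp visits.

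No printed sum is wrong. The fault is an effect assumption that does not match the schedule, together with missing information on the unit and origin of the 0.6.

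**What to change.** 1. In section 2.1a, recompute and restate power for a between-arm difference fixed at zero at T1 and T2 and starting at the camp. State the time unit of the 0.6, whether the earlier study's slope included pre-camp visits, and the assumed effect shape. State also whether 1.76 is an SD or a variance, and what site-level variance was used.
2. In section 10.1, Aim 1, unless the model notation already does so, define the H1 contrast on post-camp time and treat T1-T2 as pre-treatment measurements. Fix in advance a form that allows an effect already at T3. Examples are a camp step plus a post-camp slope, or the mean T3-T8 difference adjusted for T1-T2. A term coded 0 at T1-T3 should not be the default, because it loses power against an immediate effect.

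The cost is a rewritten power paragraph and a defined contrast, with no new data and no added enrolment. The stated power may become less favourable. Any recovery from recoding is partial and depends on the effect shape and the variance inputs.

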2.2 Inclusion and Exclusion Criteria

a) Inclusion Criteria:

Eligibility criteria for adolescent participants ("campers") include:

- (1) age between 12-17 years;
- (2) physician-diagnosed asthma that has required health service use (preventive or acute) within 12 months prior to recruitment;
- (3) persistent asthma determined by current use of a control medication or presenting at least one of the following four symptom levels in the past 4 weeks, as defined by the NAEPP guidelines ²⁸:
 - (a) > 2 days/week of daytime symptoms,
 - (b) >3-4 times of nighttime awakening,
 - (c) >2 days/week of SABA use, or
 - (d) any interference with normal activities due to asthma;

(4) no other chronic conditions requiring daily medication (e.g., diabetes, cancer, arthritis, etc.) and no severe mental illness (e.g., bipolar disorder, schizophrenia) or behavioral issues (e.g., criminal history) reported by parents or guardians;

(5) primary residence located in the participating inner cities based on zip codes; and

(6) ability to understand spoken and written English.

Eligibility criteria for peer leaders include:

(1) age between 16-20 years;

(2) nomination from school teachers/nurses or healthcare providers for candidates' exemplary asthma self-management, leadership, and emotional intelligence; and

(3) fulfillment of eligibility criteria (2)-(6) prescribed for adolescent participants.

b) Exclusion Criteria:

- 1) Adolescents who are pregnant
- 2) Have learning disabilities based on reports from teachers or clinicians will be excluded from the study because such conditions can confound the interpretation of findings.
- 3) Those who have serious health (other than asthma) and emotional preconditions (e.g., severe depression, anxiety disorders, schizophrenia)
- 4) Adolescents who become pregnant or incarcerated after enrollment will be withdrawn because these conditions can impact the study outcomes (e.g., quality of life) and limit the investigators' capacity to follow up.

3. SUBJECT IDENTIFICATION, RECRUITMENT AND CONSENT

3.1 Method of Subject Identification and Recruitment:

Participants (peer leaders and camp participants) will be recruited from a variety of settings including clinical practices, community youth organizations, schools and/or churches in the three cities using clinician referrals, recruitment letters, flyers, or newspaper or website ads. Each clinical practice/school/church from which participants will be recruited will be informed of the eligibility criteria for peer leaders, and we will provide these recruitment sites with an information sheet that includes the eligibility criteria for peer leaders and instructs that referring adults would seek permission from the parents of teens (16-17 years) they wish to refer before referral.

Referrals can be done by phone, email or written letter. In their referral, referees will provide the study team with the contact numbers of the nominated teens and their parents. Then, the study team will contact the parent/teen to screen for the nominated teen's qualification for enrollment as a peer leader. For older peer leaders (18-20 years), referees are not required to obtain parental permission prior to nomination. Older teens can also contact directly the study team responding to flyers, or newspaper or website ads to be considered as peer leaders. Each site will choose recruitment strategies that are culturally appropriate and effective in its own community. No adolescents <18 years will be allowed to participate in the study without parental permission either as a peer leader or a camper.

3.2 Process of Consent:

Group assignment will be concealed from participants and data collectors. To ensure double blinding, data collectors will not participate in obtaining informed consent, nor any part of treatments.

a) Informed Parent Permission/Consent. Consent will be obtained in a non-coercive fashion. Prior to obtaining consent, the site coordinator will provide parents/adolescents with detailed information regarding study participation. Parents and adolescents will be informed that their participation is strictly confidential, that they do not have to answer any questions they do not wish

to, and they are free to withdraw from the study at any time. The coordinator will solicit and answer any questions. When all questions have been answered, the coordinator will ask the subject a couple of questions pertaining to study procedure and the content of the consent to ensure the subject's understanding. For Spanish-speaking parents, the consent form will be prepared in their language, and an RA who is fluent in Spanish will assist obtaining the consent following the procedure described above. A parent/guardian will be asked to sign two copies of the form, and the coordinator will also sign the consent form. One copy of the form will be kept; one copy will be given to the parent/guardian.

Teen Assent. Assent will be obtained in a similar manner as the informed consent. The assent form will be written using language that is developmentally appropriate. Adolescents will be told that they do not have to answer any questions they do not wish to, and they are free to stop being in the study at any time. Adolescents will be asked to read the assent form silently while the coordinator reads the assent form to them.

b) Vulnerable populations: The coordinator will solicit and answer questions. To make certain of their understanding of the assent consent, adolescents will be asked to explain back what they are being asked to do and clarification will be provided.

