Hypothesis: We hypothesize that: relative to the control group, the PLASMA group will report greater improvement over time in (H1) quality of life (primary outcome), and (H2) asthma knowledge, attitudes, outcome expectations, self-efficacy, self-management skills, and asthma control, FEV1 (exploratory outcomes). (H3) The post-PLASMA scores on outcome measures will be higher than pre-program scores from both treatment groups.

- 2) To examine the mediating effects of the secondary outcomes (knowledge, attitudes, outcome expectations, self-efficacy, self-management skills, asthma control, and FEV1) on the primary outcome (quality of life) of the intervention.
- 3) To examine the moderating effects of personal factors (e.g., age, sex, family support) on primary and secondary outcomes of the intervention.
- 4) To evaluate the effects of PLASMA on primary and exploratory outcomes in peer leaders (16-20 years).

Hypothesis: We hypothesize that the peer leaders (n=42) will report significant improvement in quality of life (primary outcome) and secondary outcomes (knowledge, attitudes, outcome expectations, self-efficacy, self-management skills, asthma control and FEV1) over the course of 15 months.

- 5) To determine the economic impact of the intervention. This aim will be accomplished by (5a) measuring the direct healthcare costs and total costs of the PLASMA program, as compared with the control group; (5b) performing net cost analyses for each type of costs; and (5c) estimating cost-effectiveness ratios of the PLASMA group compared with the control.

Hypothesis: We hypothesize that the direct and overall costs per participant in the PLASMA group will be less than costs per participant in the control group, or cost neutral.

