Adult Led Asthma Self-Management (Control Group): The control group will attend a similar camp to the PLASMA group, which will take place within 2 weeks of the peer-led camp to minimize the history effect. Two local healthcare professionals selected by the site-PI will attend peer-leader training sessions to become familiar with the program content, then lead instructional activities. As in PLASMA, adult leaders will base their instruction on the program manual to ensure comparable program content. Campers will be divided into two age sub-groups (12-14, 15-17 years) for age-appropriate delivery of content. Adult leaders will adopt mainly a didactic format and skill demonstration. Each camper will receive the program manual. After the instructional sessions, campers will participate in "Asthma Jeopardy" and comparable recreational activities. To control for attention, the adult instructors will offer bimonthly contacts via similar contact methods to peer contacts, and will discuss topics unrelated to asthma. The study team will determine the non-asthma topics for each bimonthly follow-up to standardize interactions with participants.

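### Section 3.2 claims double blinding, but participants can see who leads their programme from camp day, so the self-reported PAQOL is not participant-blinded at T3–T8

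*Combined protocol and SAP*

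**What the plan says.** All references are to the combined protocol and SAP.

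- **Blinding (3.2, Process of Consent).** "Group assignment will be concealed from participants and data collectors". The means follows at once: "To ensure double blinding, data collectors will not participate in obtaining informed consent, nor any part of treatments".
- **Camps (4.1, Design).** "Each group will attend a separate day camp where an asthma self-management program will be implemented either by peer leaders (intervention) or healthcare professionals (control".
- **Contacts after camp (4.1, Design).** In one arm, "the intervention group will receive peer-leader contacts bimonthly for 14 months". In the other, "Adult instructors (healthcare professionals) will contact the control group bimonthly for 14 months using similar methods, but different contact topics". The control-group paragraph of 4.1 adds that the adult instructors "will discuss topics unrelated to asthma".
- **Primary outcome (1, hypotheses for Aim 1).** The expectation is that "the PLASMA group will report greater improvement over time in (H1) quality of life (primary outcome". Section 7 says questionnaires are completed online, and 7.2 classes them as self-reported.
- **Timing (4.1, Design).** Teens are randomised upon enrolment. T1 is at enrolment, T2 three months later, T3 straight after the camp, and T4–T8 at 3 to 15 months after it.

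**The concern.** Section 3.2 claims a property that the design in 4.1 cannot have once the camps begin. Leader type is the intervention, and it is visible to everyone who attends. The one measure offered in support, separating data collectors from consent and treatment, acts on staff and not on participants. For PAQOL the participant is the assessor, so masking staff does not mask the primary outcome.

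What is at stake is the interpretation of the main result. A reader told that the trial is double-blind would give a PAQOL difference more protection against reporting bias than it has. There is also a practical gap before camp. Randomisation precedes T2, but no section says when teens learn which camp they will attend. If they learn early, T2 is exposed too. Attendance could also be affected: section 5 withdraws teens who do not come to camp, and section 2.1(a) reports that 13 of 55 in the earlier inner-city subsample did not attend.

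**Working it through.** The plan gives no figure on blinding to reproduce. The check sets its statements side by side, followed by a short illustration.

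**1. Can participants be masked after camp?** A camper attends one of two separate camps and sees whether peers or professionals run it. The later contacts come from a peer or from an adult, and the adult contacts avoid asthma. PLASMA teens also rate their peer leaders at the camp (4.1, program evaluation measures, item c). Nothing described in 4.1 hides leader type.

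**2. Which assessments are affected?** T1 and T2 precede camp; T3 to T8 follow it. That is 8 − 2 = 6 of 8, and these carry most of the treatment-by-time contrast in the Aim 1 model (10.1).

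**3. How large could the effect be?** The documents give no estimate of reporting bias, so the 1-unit shift below is an assumption chosen for scale.

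Inputs: treatment-by-time coefficient 0.6 units, with no time unit stated (2.1(a)); eight time points, hence seven intervals (2.1(a), 4.1); data collection over 21 months (7.2).

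| Time coding | Implied end difference | 1-unit shift as a share |
|---|---|---|
| Per interval, 0–7 | 0.6 × 7 = 4.2 | 1 / 4.2 = 24% |
| Months, 0–21 | 0.6 × 21 = 12.6 | 1 / 12.6 = 8% |

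The same shares result if the shift is constant from T3 on and is fitted as a slope with complete, equally spaced data:

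- Per interval: slope = Σ(t − 3.5) over T3–T8 / Σ(t − 3.5)² over T1–T8 = 6 / 42 = 0.143, and 0.143 / 0.6 = 24%.
- In months: slope = (3 × 6) / (9 × 42) = 18 / 378 = 0.048, and 0.048 / 0.6 = 8%.

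**4. Is data-collector blinding secure?** The role descriptions do not fit together.

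| Section | Role described |
|---|---|
| 3.2 | Data collectors take no part in consent or treatment |
| 3.2(a) | The site coordinator obtains consent; a research assistant helps with Spanish-speaking parents |
| 4.1, Design | The project coordinator and a research assistant handle recruitment and consent |
| 4.1, Design and control group | Adult instructors make the control contacts |
| 4.1, control fidelity | The research assistant makes the control contacts |
| 4.1, measures, item (j) | Research assistants visit homes to download peak-flow data |
| 8 | Coordinator and peer leaders need contact details for data-collection follow-up visits |

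The same job titles appear under consent, treatment contact and data collection, which 3.2 says are kept apart.

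**The case against.** The strongest reply is that seeing the leader is not knowing the hypothesis. Both arms get a day camp, the same manual, the quiz game, comparable recreation and attention-matched contacts, and each teen sees only one format. This stands as a limit on the likely harm. It does not rescue the claim in 3.2, which is that assignment itself is concealed, and the protocol describes no masking to the hypothesis. I have not seen the consent and assent forms, which may show what teens are told.

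A reader might infer that peer-led teens will inflate their scores to please their leaders. The documents do not support that direction. Section 7 describes individual logins, answers sent straight to the study centre and no access for other users. The peer follow-up paragraph of 4.1 places data collection before peer contact at 6 and 12 months. Control teens could equally give pleasing answers to health professionals.

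It can also be said that the sentence sits under consent and so means allocation concealment, or simply non-disclosure before camp. That reading is possible for T1 and T2, but the text names participants and uses the term double blinding without a time limit. Finally, participant blinding is not feasible here. That is agreed, and none is asked for; the point concerns an accurate description.

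**Conclusion.** The statement in 3.2 is wrong as written. PAQOL is not participant-blinded to leader type at T3–T8, six of eight assessments. It would go too far to call the primary outcome unblinded throughout: T1 can be blind, and so can T2 if camp type is withheld.

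Neither the size nor the direction of any bias can be derived. The 24% and 8% figures rest on an assumed 1-unit shift and on two readings of an unstated time unit; 4.2 units is not a planned difference stated anywhere in the plan. A reader might also infer from the overlapping job titles that data collectors are in fact unblinded. The documents do not show that the same individuals fill these roles, only that the sections need reconciling. The design can stand; the claim, and any reading of PAQOL as a blinded outcome, cannot.

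**What to change.** 1. In 3.2, replace the double-blind claim with: *Participants are not blinded to leader type from the camp onward; data collectors are blinded.* Do not interpret PAQOL as a blinded outcome. The second clause depends on item 3.
2. Because randomisation takes place upon enrolment, state that camp type is not disclosed to participants until T2 is complete. This protects both pre-camp scores. Holding it back until arrival would also remove any influence on camp attendance.
3. Reconcile 3.2, the Design, control-group, control-fidelity and peak-flow paragraphs of 4.1, and section 8, so that no one who obtains consent or makes treatment contacts also collects outcome data. Claim analyst blinding only if it will be done; no section provides for it now.
4. In reporting, set PAQOL beside the less self-rated measures already collected: claims-based utilisation, spirometry and dose counters. Present them as supportive context. None measures quality of life, spirometry and dose counters are described as taken only twice, and the first spirometry is described as taken at the camp.

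The cost is wording, a small disclosure rule and a clearer division of staff duties. No outcome, model or sample size changes. The downside is a less favourable description of the design.
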